Purpose: The two prominent OAs used in treating obstructive sleep apnea (OSA) differ in their designs, MT versus BT. From a clinical perspective, it is important to know which design is superior and should be the 'treatment of choice' for improving airway function and sleep quality. These two designs differ in their protrusive mechanisms that are categorized in general under four main types: bilateral compression, bilateral traction, midline compression and midline traction. Although the two designs considered in this proposal have undergone the most rigorous testing individually, well controlled 'head-to-head' trials as proposed here have not been conducted to determine their efficacy within a single test population.

Patients/Methods: Adults (n=44) with moderate to severe OSA diagnosed by polysomnography (PSG) or home sleep test (HST) within the previous year, who are using CPAP therapy, will be recruited and selected to enter the study. The study duration will be approximately nine months and each patient is expected to participate in the study for nine consecutive weeks. The first 4-weeks involve using one of either MT or BT OAs followed by 1-week washout period, then 4-weeks using the second OA. Home sleep recordings will be collected at T_1 -first OA start; T_2 -end first OA; T_3 -second OA start; T_4 -end second OA. The primary outcome measure will be the respiratory disturbance index (RDI).

Table 1: Examples of sequela associated with OSA in adults.

Health Consequences	Adult
Excessive daytime sleepiness	√
Reduced Quality of Life	√
Accidents (i.e. occupational, motor vehicular)	√
Hypertension	\checkmark
Cardiovascular disease	√
Obesity	√
Neuromuscular disorders	\checkmark
Sleep quality	√
ADHD	\checkmark
Learning difficulty; Cognitive impairment; Dementia; Alzheimer's	√
Disease	
Behavior problems	\checkmark
Sleep-walking	\checkmark
Hormonal & metabolic problems	\checkmark
Bruxism	√
Depression	√
Impotence	√

Table 2: Select oral appliance studies using midline traction and bilateral thrust

	al appliance studies using iniu					
			pre			%
Device	Study	post AHI	AHI	#pts		improvement
TAP -MT	Hoekema2007a	3.2	20.4	20	Moderate	84%
TAP - MT	Hoekema2007b	5.2	50	9	Severe	90%
TAP - MT	Hoekema2008a	4	31	12	Severe	87%
TAP - MT	Hoekema2008b	7.8	39.4	51	Severe	80%

TAP - MT	Holley 2011*	8.4	30	497	Severe	72%
TAP - MT	Ghazal 2009	7.9	22.2	48	Moderate	64%
Somnodent - BT	Deane 2009	12	27	22	Moderate	56%
Somnodent - BT	Gotsopoulos 2002	12	27	73	Moderate	56%

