b. Population

- 1. Adults (n=44) with moderate to severe OSA.
- 2. Potential study participants will be recruited by means of flyers posted at the College of Dentistry, Dallas A.W.A.K.E. office (support group for sleep apnea patients) and Dallas area sleep clinics. Online postings at clinicaltrials.gov and the College web site. Also post flyers at (1) regional hospitals and clinics, (2) city and county offices/stations (such as the Dallas Fire Department), (3) DART and other transportation offices and (4) Facebook, Twitter and similar site, (5) local newspapers and magazines, (6) local radio stations. The content of the advertisements on venues (5) and (6) will be the same as the approved flyers. Written permission will be sought from all sites at which flyers are to be posted. Data analyst and subjects will be blinded to treatment device type (i. e. sequence of use of the two OAs) and subject's identity will be coded.
- 3. Controls and Controlling Confounders: Subjects serve as their own controls; their baseline polysomnography (PSG) or Home Sleep Test (HST), untreated values (from full or split night PSGs) will serve as their control values for evaluating treatment effects with each of the two OAs. The focus of the trial is on comparing OA appliance efficacy in reducing the RDI (AHI); the presentation, fitting, monitoring and adjustment of the two OAs will be the same for both arms of the study. For the operators, there will be concealed allocation of assignment of subjects to treatment.
- 4. Performance Site: Texas A&M College of Dentistry, [name]. Seventh floor room 725, two operatory clinic.

c. Inclusion criteria

OSA diagnosed adults, at least 18 years old, who have been recently diagnosed by polysomnography (PSG) or polygraphy home sleep test (HST) in the previous year and are currently being treated with continuous positive airway pressure (CPAP) having an AHI > 15 events/hour of sleep; two or more OSA symptoms (snoring, witnessed apnea or daytime hypersomnolence complaint); at least 8 teeth per arch to support either OA device; Mallampati score from I to III; Palatine tonsils – grade 0, 1, or 2; Central and mixed apnea index < 5 events /hour. Consent to study's timeline; willingness to wear home sleep test apparatus for at least 4 nights and to wear an oral appliance every night for 8 weeks; willingness to pick up and return home sleep test kits as needed.

d. Exclusion criteria

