Cardiac & pulmonary disease (e.g., congestive heart failure, severe arrhythmias, COPD); central sleep apnea; comorbidities of other sleep disorders other than OSA; no active TMD or jaw muscle pain, morphological airway abnormalities, BMI ≥35; pre-existing difficulty swallowing; throat or neck related health issues; endocrine dysfunction; severe psychiatric disorders; intellectually disabled; previous OA therapy; previous ENT surgery; restrictions in jaw opening; pregnant / breast feeding or intent to become pregnant during the study; inability to provide informed consent and apply the HST recorders.

e. Table 4: Variables of Interest: Primary, Secondary and Exploratory

Prima	ry	Secondary	Exploratory
with f of-tre secon treatn OA; T	art-of-treatment irst OA; T ₂ -end-atment with d OA; T ₃ -start-of-nent with first f ₄ -end-of-nent with second	T ₁₋₄ Snore count; OA compliance; Mean disease alleviation; Sleep Quality T _{0, 2, 4} Epworth Sleepiness Scale score; Short Form-36 score Thornton snoring scale Sleep observer scale Symptom alleviation Changes in occlusion as measured by shim stock, tested before and after	T ₄ OA device preference and perceptions of comfort; Development of a cost effective titration protocol with maximal patient convenience.

Mean disease alleviation is a composite measure of the reduction in RDI and OA compliance. RDI, respiratory disturbance index equals the number of respiratory events per hour of recorded time; $T_{1,4}$, time points 1-4

- f. Data collection techniques to be used during sleep
 - 1. OA compliance
 - i. This variable is determined by the number of hours that the OA device is worn per hour of sleep per night using Braebon monitors (integrated chips; Kanata, Ontario, Canada)
 - 2. Respiratory measures (Figure 3)
 - Braebon polygraphy (PG) recorder for home sleep testing: airflow, respiratory effort, electrocardiogram (ECG), pulse oximetry, anterior tibialis electromyography, body position, and snore sound.

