The PG unit is a category Type III sleep testing device. Manually scored sleep disordered breathing events will be categorized as apnea or hypopnea (RDI; ≥ 5 , >15, >30 events/hour) and phenotyped as either obstructive or central type events. Mixed events will be assigned to the OSA category. The definition of apnea to be used will be a $\geq 90\%$ reduction in airflow from baseline and ≥ 10 seconds in duration. Hypopnea will be defined as a reduction in airflow of $\geq 30\%$ with an associated oxygen desaturation. The RDI will be defined as the number of apnea-hypopnea events divided by recorded hour. $^{3, 24}$

- 3. Sleep quality assessment (Figure 4, 5)
 - SleepImage (MyCardio, LLC, Broomfield, CO) recorder: ECG, actigraphy, body position, snore, ECGderived respiration

The SleepImage system includes a sleep recorder that is clinically validated and FDA cleared to allow the non-intrusive collection of objective measures of sleep quality. The ECG-recorder with cardiopulmonary coupling (CPC) analysis collects ECG, actigraphy, snoring and body position data at a sampling rate of 600 Hz that is later filtered to sampling rates of 200, 40, 10 and 10 Hz, respectively. The ECG-recorder's sleep data are uploaded and scored automatically. CPC algorithms assess the ECG's R-wave amplitude change associated with tidal volume dynamics to derive a respiration (ECG-derived respiration) signal. The resulting sleep spectrogram, divides sleep states into "stable sleep" (0.1–0.4 Hz) and "unstable sleep" (0.01–0.1 Hz). Within 0.01-0.1 Hz is the "narrow band" that identifies central-periodic type patterns (0.006–0.1 Hz) and obstructive type events primarily through a "broadband" (0.0–0.01 Hz, not fitting narrow band criteria) pattern. ^{27, 28} Between-treatment differences in the proportions of stable and unstable sleep will be evaluated.

Subjective measures related to the sleep experience of the subjects will also be collected using these questionnaires at T_0 , T_2 and T_4 : Eppworth sleepiness scale, Quality of Life Short Form-36, version 2 and the Thornton snoring Scale.

g. Data collection

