Wilcoxon signed-rank test (matched pairs) for cross-over design for primary variables will be used. For dichotomous secondary variables, data analysis will use logistic regression to adjust for effects of initial severity, age, gender, BMI, ethnicity, SES, phenotypic differences, etc. t-tests and Mann-Whitney tests as needed for non-dichotomous outcomes, depending upon normality. Descriptive statistics (means, standard deviation, medians, interquartile ranges) for each outcome measure will be calculated and bar, boxplot or line graphed for each time point. Repeated measures analysis of variance, parametric or nonparametric one-way analysis of variance, as appropriate, will be used to determine if each of the outcome measures vary across the time points.

1. Handling of missing data

For the primary study endpoint, several methods will be used, including: 1) last observation carried forward, 2) multiple imputations, and 3) imputing a missing value with the group's mean value at that follow-up and frequency.

The set of missing data analyses will serve as a sensitivity analysis for the primary study outcomes. If the data imputation methods for a given endpoint result in disparate statistical inferences, the differences will be investigated and elucidated in the final clinical study report.

j. Right and Safety of Research Participants

The clinical trial will be conducted in accordance with the ethical principles that have their origin in the Declaration of Helsinki and the Belmont Report and that are consistent with Good Clinical Practice (GCP). The laws, regulations and rules of the United States, the state of Texas and the Texas A&M University pertaining to human subjects research will be followed. The rights, safety, and well-being of the trial subjects are the most important considerations and will prevail over the interests of science and society. The available clinical information on the OA devices is adequate to support the proposed clinical trial.

Freely given informed consent will be obtained from every subject prior to clinical trial participation. All patient clinical trial information will be recorded, handled and stored in a way that allows its accurate reporting interpretation and verification. The confidentiality of records that could identify subjects will be protected, respecting the privacy, confidentiality rules and to ensure non-bias reporting requirements.

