d. Table 6: Protocol For Pre-OA Evaluations

EVALUATION	PURPOSE	PROCEDURE/RATIONALE
Pre-study AHI	Subject's own baseline AHI data for comparison to OA response	PSG or PG conducted within up to 1 year before study inclusion for baseline AHI/RDI
Pre-study questionnaire	Quality of life questionnaire for comparison to OA response	Complete the Epworth sleepiness scale and quality of life or functional outcomes sleep questionnaire. This data will be performed on the same day as sleep studies $(T_{1\text{-}4})$.
Snore Index	Baseline snore index for comparison to OA response	Data collected as a part of PSG.
Number of Periodic Limb Movements (PLMS)	Baseline number of PLMS with arousals to determine study inclusion or exclusion	Data collected as a part of PSG. This is a study exclusion criteria.
Number of Central Sleep Apnea (CSA) events	Baseline number of CSA events to determine study inclusion or exclusion	Data collected as a part of PSG. This is a study exclusion criteria.

Table 4: Protocol for OA use and home sleep recordings

TASK	PURPOSE	PROCEDURE/RATIONALE
Oral Appliance, Home Sleep Test and	To instruct subjects on how to apply, use, care for, remove	Explain and demonstrate OA use; provide instructions regarding the correct application and
SleepImage recorders orientation	and return the OAs, sleep recorders to obtain optimal recordings.	removal of HST electrodes and sensors. To provide instructions on care and return of study equipment for optimal data collection and timely return of equipment.

Completion of sleep diary and questionnaires	To instruct participants on how and when to complete the sleep diary and questionnaires.	The proper completion of the sleep diary and questionnaires facilitates assessment of the study's secondary outcome measures.
Adverse Device Effects reporting	To instruct the study subject on the definition of an Adverse Event and how to report an event.	To ensure the study subject's safety and health, whether or not the changes are believed to be device related.

References

- 1. Punjabi N. (2008) The Epidemiology of Adult Obstructive Sleep Apnea. Proc Am Thorac Soc. 5(2): 136-143.

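### Pre-study questionnaire scores are, by inference, on-CPAP values, so change from T0 estimates the oral appliance relative to prior CPAP, not symptom response to the appliance

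*Combined protocol and SAP*

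**What the plan says.** All places below are in the combined protocol and SAP, section 12.1, unless noted.

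- **Treatment at entry.** The abstract describes adults "who are using CPAP therapy, will be recruited and selected to enter the study". The inclusion criteria (VII.c, repeated in section 13.4) require patients who "are currently being treated with continuous positive airway pressure (CPAP"). The first appointment (IX.b) covers records, intake assessment, consent and impressions. It mentions no interruption of CPAP. The one-week washout between appliances also uses CPAP nightly (VII.g).
- **Questionnaire schedule.** VII.f.3 says: "Subjective measures related to the sleep experience of the subjects will also be collected using these questionnaires at" T0, T2 and T4. The instruments are the Epworth scale and "Quality of Life Short Form-36, version 2 and the Thornton snoring Scale". Table 4 (VII.e) lists "Epworth Sleepiness Scale score; Short Form-36 score", the Thornton scale, a sleep observer scale and symptom alleviation as secondary variables at the same three points.
- **Role of the pre-study questionnaire.** Table 6 (IX.d), on pre-OA evaluations, states the purpose as "Quality of life questionnaire for comparison to OA response". On timing it says "This data will be performed on the same day as sleep studies", with T1-4 in brackets. It names a quality-of-life or functional-outcomes instrument instead of the SF-36.
- **RDI baseline.** VII.b item 3 takes untreated PSG or home sleep test values as the control values.
- **Analysis.** In VII.i, repeated-measures or one-way ANOVA "will be used to determine if each of the outcome measures vary across the time points". The matched-pairs Wilcoxon test is named for primary variables. For non-dichotomous outcomes the section lists t-tests and Mann-Whitney tests.

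**The concern.** Table 6 gives the pre-study AHI, the baseline snore index and the pre-study questionnaire the same role, as the reference for OA response. The AHI reference is a night without treatment, and the snore index comes from the PSG. The questionnaire reference is, as far as the text shows, a period on CPAP.

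A report that follows the plan could therefore set an RDI reduction from untreated disease beside a symptom change from CPAP-treated disease, and present both as response to the appliance. If CPAP had already relieved symptoms, the questionnaires could show little change or a decline even though both appliances work. At stake are the secondary questionnaire outcomes when they are read as change from T0, and the questionnaire part of Objective 3 (sleep quality changes with OA use). The Study Limitations name the lack of a placebo device but do not mention this.

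**Working it through.** The plan gives no figure on this point, so there is none to reproduce. The check traces treatment state through the schedule and then decomposes the change from T0.

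**Treatment state at each reference or assessment**

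| Measure | Reference or assessment | Treatment state |
|---|---|---|
| AHI/RDI control value | Diagnostic PSG or home test | Untreated (stated, VII.b) |
| Snore index, baseline | PSG (Table 6) | Untreated, following VII.b |
| Epworth, SF-36, Thornton scale | T0 | On CPAP (inferred: eligibility, and no off-period described) |
| Same questionnaires | T2, T4 | On first OA, on second OA |
| SleepImage measures | T1 to T4 | On OA; no T0 value used |

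No questionnaire is scheduled in an untreated state, either before the first appliance or in the washout.

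**Decomposition.** Let C, M and B be the mean improvement over untreated from CPAP as actually used, from MT and from BT.

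- Change from T0 on MT = M − C
- Change from T0 on BT = B − C
- MT minus BT = (M − C) − (B − C) = M − B, so T0 cancels

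**Illustration.** The values M = 5, B = 4 and the range of C are assumptions; the documents give none of them.

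| C | MT change from T0 | BT change from T0 | MT − BT |
|---|---|---|---|
| 0 | 5 | 4 | 1 |
| 2 | 3 | 2 | 1 |
| 4 | 1 | 0 | 1 |
| 6 | −1 | −2 | 1 |

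The benefit over untreated is 5 and 4 in every row. Only the reference moves. The row C = 0 is the limit in which CPAP is prescribed but hardly used.

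**What the test across time points would see.** Suppose T2 and T4 are each pooled over devices, the two sequences are equal in size and there is no period effect. The mean gain over untreated is then (5 + 4)/2 = 4.5 at both T2 and T4. Their difference from T0 is 4.5 − C, which is 4.5, 2.5, 0.5 and −1.5 for the four rows. T2 and T4 do not differ, so on that reading the test is driven by T0 against the two OA points, which is the contrast that depends on C.

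**The case against.** The strongest reply is that CPAP use at T0 is an inference. T0 is not defined in the text, and the schedule figure cited in section IX was not available to me and may define it. IX.b sends patients without a current PSG home with a home sleep test for comparable baseline data, so some may have at least one night off CPAP. This stands as a limit on certainty. It does not supply an untreated questionnaire period, and the plan describes none.

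Second, a score taken before OA use in CPAP users is a legitimate before-and-after reference, and both hypotheses concern RDI, MT against BT. That is correct. The comparison is usable if it is named as OA relative to CPAP; the difficulty is the label in Table 6. VII.i also names no change-from-T0 test. It refers only to variation across time points, and the comparator role comes from Table 6.

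Third, entry requires at least two OSA symptoms. If these are current symptoms, T0 is not a fully relieved state and improvement can still be seen. Poor CPAP adherence works the same way, moving T0 nearer to untreated. Both points make the size uncertain without changing what is being estimated.

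A reader might go further and infer three things that the documents do not support:

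- *That the questionnaires will show no change or worsening.* This depends on C, which is unknown.
- *That all of Objective 3 lacks a valid comparator.* The SleepImage part is planned as a between-treatment comparison and does not use T0.
- *That Table 6's timing puts the baseline questionnaire after OA exposure.* A form completed on the day of T1 may precede that night. The T1-4 against T0, T2, T4 conflict is a separate matter that needs reconciling.

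**Conclusion.** The point holds in a limited form. As written, the plan treats what are most probably on-CPAP questionnaire scores as the reference for OA response, beside an AHI/RDI reference that is untreated. Change from T0 in Epworth, SF-36 and the Thornton scale therefore estimates OA relative to prior CPAP as used. It could understate, cancel or reverse the apparent symptom benefit by the amount C, which the documents do not allow one to estimate.

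This rests on two assumptions: that patients who must be current CPAP users are still using it when they complete the first questionnaires, and that change from T0 will be read as OA response, as Table 6 implies.

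The primary RDI endpoint, the SleepImage measures, the PSG-based snore index and the MT-versus-BT contrast are unaffected. A reader should not infer bias in the trial's main comparison. The matter should be corrected because it decides what may be concluded from the secondary questionnaires.

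**What to change.** 1. Define T0 and state that questionnaires at that point are completed on CPAP.
2. Make the main questionnaire analysis the within-subject comparison of MT with BT at the end of each 4-week period (T2 against T4, with the sign assigned by device). Use a paired test. VII.i now names a matched-pairs test only for primary variables, and a Mann-Whitney test would ignore the pairing.
3. Report change from T0 to T2 or T4 only as OA relative to CPAP, not as OA response or as symptom alleviation against untreated OSA. Reword the purpose entry in Table 6 to match, and add the point to the Study Limitations.
4. Reconcile Table 6 (T1-4; a quality-of-life or functional-outcomes questionnaire) with Table 4 and VII.f.3 (T0, T2, T4; SF-36).

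The cost is wording and analysis text only, with no extra visits. The downside is that the trial makes no claim of symptom benefit over untreated OSA, a claim that the design as described could not support in any case.

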 Thomas RJ, Mietus JE, Peng CK, Gilmartin G, Daly RW, Goldberger AL, Gottlieb DJ. obstructive from central and complex sleep apnea using an automated electrocard Sleep; 30:1756-1769. 	
{GO TO ATTACHED PROTOCOL FILE TO VIEW THE FOLLOWING CORRECTLY}	
Figures 1 and 2	
Figure 1. TAP 1 Oral Appliance (MT Style) Figure 2. SomnoDent Flex C	oral Appliance (BT Style)
Figure 3: Home Sleep Test device in recording position. Figure 5: Sleepimage sleep device actual size. Figure 4: Sleepimage sleep device in recording position.	
Will audio recordings be collected?	
O Yes • No	
Will visual images be collected?	
○ Yes • No	
If visual images will be collected, are they full, facial identifiable images?	
C Yes No	

12.3 Other Committee Approvals	
Select all that apply.	
▼ None	
☐ Animal Use ☐ Biohazards	
_	

☐ Chemical ☐ Radiation ☐ Other
If any committee approvals apply, please provide the permit number and approval date.
13.0 Study Population
13.1 Number of Participants
Approximately how many subjects do you plan to enroll?
38
Provide the rationale for the number of subjects requested (for example, power analysis, sponsor requirements, etc.).
Approximately 38 subjects must complete the study to yield a power of 0.90 with alpha = .05 and an expected Effect Size of at least a 10 point difference in the post-treatment mean RDI scores between MT vs. BT devices. Recruitment will be extended to n=44 to accommodate a 10-20% drop-out rate. The projected numbers are based on Wilcoxon signed-rank test where the expected difference between-treatments (cross-over design) is expected to be at least a 10 point difference in RDI scores. As many as 44 will be enrolled to account for attrition.
Will human subjects be used from the Qatar population?
○ Yes • No
* If Yes, then approval by an IRB in Qatar may also be required.
Will human subjects be used from another international population?
C Yes O No
*If Yes, then approval by an international review board or government may also be required.
Will human subjects be used from a Native American population?
O Yes ⊙ No
*If Yes, then approval by a tribal IRB(s) may also be required.
If Yes for research in Qatar, in another country, or with Native Americans, provide justification for that research being conducted in that particular community.
13.2 Provide the age groups being enrolled into this study (Note the consent documents required for each age group listed in parentheses):
 □ 0-6 (parental consent only, Pediatric Assessment required for Clinical Trials) □ 7-11 (child's assent plus parental permission, Pediatric Assessment required for Clinical Trials) □ 12-17 (consent plus parental permission, Pediatric Assessment required for Clinical Trials) ▼ 18+ (consent only)
Enter the specific age range for study population (if overlap or specific within a category):

13.3 Indicate the gender of participants being enrolled into this study:	
MaleFemale✓ Both male and female	

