Treatment devices: TAP 1 (Airway Management Inc., Dallas, TX; MT type OA device) and SomnoDent Flex (SomnoMed, Plano, TX; BT type OA). Both OA devices will be used per manufacturers' recommendations. To insure comparability, both devices have a custom thermal acrylic liner insuring a very accurate fit. Each subject will also be custom fitted with a mandibular positioner ("AM Aligner" or "Morning Positioner") to use for up to 20 minutes after awakening in the morning; this will assist in returning the subject to his/her normal occlusion.

Appliance Acclimation: Both appliances will be adjusted / titrated to the patient's maximal comfortable protrusive position by patient in the wake state. The starting position will be determined by the patient at a comfortable position but not less than 60% as determined by the Pro Gauge. "Comfortable" is defined as the advanced mandibular position that permits the subject to sleep for ≥ 5 hours per night for at least 6 nights of the week. Subjects will use diaries to record appliance settings and hours of sleep on each sleep recorded or non-recorded night. Two follow-up nights (post T_1) of SleepImage recordings only will be made to track sleep quality and OA position, if further mandibular adjustments are necessary as determined by the T_1 & T_3 HST and SleepImage results.

Course of Treatment: Subjects will be randomly assigned to either the MT- or BT-first OA device as treatment for OSA. Each subject will use the first OA for 4 weeks followed by – 1 week washout period that includes using nightly their prescribed CPAP and daytime use of a mandibular positioner (for up to 20 minutes) – then another 4 weeks of active treatment with the second OA.

h. Power Analysis and Sample Size

At least 38 subjects with OSA are needed to yield a power of 0.90 with alpha = .05 and an expected Effect Size of at least a 10 point difference in the post-treatment mean RDI scores between MT vs. BT devices.Recruitment will be extended to n=44 to accommodate an estimated 20% drop-out rate. The projected numbers are based on Wilcoxon signed-rank test where the expected difference between-treatments (cross-over design) is expected to be at least 10 point difference in RDI scores.

i. Statistical analyses

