13.6 Experience of Subjects	
Describe the experience of subjects while participating in this research. (Please describe what the participant will experience from the time of learning of the study through completion.) After meeting the study's inclusion and exclusion criteria through direct or telephone screening, prospective participants will receive detailed information about the study from the study coordinator during their first appointments. They will have an opportunity to have all of their questions about the study answered to their satisfaction by the coordinator and investigators. Those individuals who give informed consent will be enrolled in the study. The first appointment to the study center will include obtaining a copy of the patient's polysomnogram/continuous positive air pressure (PSG/CPAP) study reports and medical history, completion of the study's intake assessment. In the absence of a current PSG, subjects will be sent home with a HST to collect comparable baseline information. During this approximately 2-hour first appointment, the prospective subject will be given an oral exam by one of the	

team dentists to insure that the dentition, periodontium, temporomandibular joints, muscles of

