mastication are sufficiently healthy and stable for the safe participation in the study. If determined to be sufficient, the subject will then be fully enrolled in the study and have the study and tasks explained in greater detail. Dental impressions will then be obtained to prepare models for the fabrication of the custom oral appliances. Protrusive bite registrations will also be made at this time. Both oral appliances (OAs) will be constructed prior to the second appointment. During the second appointment, subjects will be examined and fitted by one of the study dentists with both OAs; if modifications are needed to improve fit, an OA may be sent back to the lab. The subjects will be assigned to one OA or the other at this second appointment according to predetermined randomization scheme. Neither the dentist nor the subject will know the assignment until the actual delivery. Subjects will be then scheduled within 4-weeks for the first home sleep study (HST, Medibyte system) with simultaneous SleepImage (SI) recording for determination of the Relative Disease Index (RDI) and sleep quality criteria. Recordings will occur x1 /subject at T_1 (first night in week-1 with first OA), T_2 (after four weeks using first OA), a washout period of 1 week using a mandible repositioner daily and CPAP nightly, T_3 (first night of week-6 with second OA) and T_4 (after four weeks using second OA) (Figure 1; Table 1).

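### Section 13.1 enters 38 as the planned enrolment, but 38 is the number who must complete; the same section and the embedded protocol enrol 44

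*Combined protocol and SAP*

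**What the plan says.** The form question in section 13.1, "Approximately how many subjects do you plan to enroll", is answered with 38. The rationale in the same section uses 38 differently: "Approximately 38 subjects must complete the study to yield a power of 0.90 with alpha = .05". It continues "Recruitment will be extended to n=44 to accommodate a 10-20% drop-out rate" and ends "As many as 44 will be enrolled to account for attrition".

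The protocol embedded in section 12.1 agrees with the rationale. Section VII.h states "At least 38 subjects with OSA are needed to yield a power of 0.90 with alpha = .05" and extends recruitment to 44, there for an estimated 20% drop-out. The abstract and section VII.b describe the population as "Adults (n=44) with moderate to severe OSA".

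So 38 appears as the number needed or completing in VII.h and in the 13.1 rationale, and as the number to enrol only in the 13.1 answer field. Every other statement of how many will be recruited or enrolled gives 44.

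**The concern.** A completer requirement and an enrolment target are different quantities, and the gap between them is the drop-out allowance. Entering the first as the second removes that allowance. Anyone who takes the planned sample size from the answer field, such as an IRB member or someone preparing a summary of the application, would read a trial of 38 with no margin for loss. On that reading a single drop-out takes the trial below the number on which its stated power rests.

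The entry is a stated sample size, so it deserves correction even though the intended figure can be recovered from the lines below it.

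**Working it through.** **Inputs from the documents.** Enrolment answer 38 (13.1). Completers required 38, power 0.90, alpha 0.05 (13.1, VII.h). Difference to detect: 10 RDI points, paired, by Wilcoxon signed-rank test (13.1, VII.h). Drop-out 10-20% (13.1), 20% (VII.h). Recruitment 44 (13.1, VII.h, abstract, VII.b).

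**Not in the documents.** The SD of the paired differences, and whether alpha is one- or two-sided.

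**1. Can 38 be reproduced?** No. Under the paired normal approximation, n = ((z_alpha + z_power) x SD / 10)^2, so n depends on the missing SD. For a two-sided test at power 0.90, an assumed SD of 10 gives 11 to 12 pairs and an assumed SD of 25 gives 66 to 69. In each pair of figures the larger value includes the signed-rank efficiency factor 3/pi.

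**2. SD implied by the plan's own claim.** Take 38 pairs at power 0.90 as given and solve for the standardised difference d = 10/SD.
- Two-sided normal: d = (1.960 + 1.282)/sqrt(38) = 0.526, SD = 10/0.526 = 19.0.
- With the 3/pi factor: d = 0.538, SD 18.6.
- Paired t: d = 0.540, SD 18.5. With the 3/pi factor: d = 0.553, SD 18.1.
- One-sided: d between 0.475 and 0.495, SD from about 21.1 down to about 20.

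**3. Completers if 38 are enrolled.** 38 x 0.90 = 34.2, and 38 x 0.80 = 30.4. If losses are independent, the chance that all 38 complete is 0.90^38 = 0.018 at 10% drop-out and 0.80^38 = 0.0002 at 20%.

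**4. Power at those numbers.** With d held fixed, power = Phi((z_alpha + z_power) x sqrt(n/38) - z_alpha). In the normal approximation the SD cancels, so the result depends only on n/38 and on sidedness. For example, two-sided with n = 34: 3.242 x sqrt(34/38) - 1.960 = 1.106, power 0.866.

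| Calculation | 38 completers | 34 completers | 30 completers |
|---|---|---|---|
| Normal, two-sided | 0.900 | 0.866 | 0.821 |
| Normal, one-sided | 0.900 | 0.869 | 0.830 |
| Paired t, two-sided | 0.900 | 0.864 | 0.816 |
| Paired t, one-sided | 0.900 | 0.868 | 0.827 |
| Paired t with 3/pi, two-sided | 0.900 | 0.863 | 0.815 |
| Paired t with 3/pi, one-sided | 0.900 | 0.868 | 0.827 |

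Simulated two-sided signed-rank tests at SD 18.1 gave 0.90, 0.86 and 0.81. At SD 18.6 they gave 0.885, 0.835 and 0.796. They start below 0.90 because the normal approximation is slightly optimistic for this test, so 18.1 is the better calibrated of the two values.

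**5. The same check for 44.** At 10% drop-out 44 x 0.90 = 39.6 completers, power about 0.91. At 20%, 44 x 0.80 = 35.2, power about 0.875. Retaining 38 needs 38/0.90 = 42.2, so 43, or 38/0.80 = 47.5, so 48. Enrolling 44 keeps 38 completers up to a loss of 1 - 38/44 = 13.6%.

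**The case against.** The strongest reply is that the section corrects itself. The question asks for an approximate number, and the rationale a few lines below separates completers from enrolled subjects and names 44 twice. Its wording can be read as a base of 38 that is extended as losses occur, up to 44. On that reading there is no shortfall caused by stopping at 38, because recruitment does not stop there. This stands as far as practical weight goes. It does not make the field right: VII.b and the abstract give 44 outright, and an approximate completer count is still not an enrolment count.

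A reader might infer three stronger points that the documents do not support.

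- **That the trial cannot reach 0.90 power.** This would need enrolment to stop at 38 and at least one subject to be lost. No section tells the investigators to stop at 38, and 38 enrolled with no loss would meet the stated basis.
- **That enrolling 44 would overrun the approved figure.** The application itself gives 44, in 13.1 and in the embedded protocol. Section 26.1 requires amendments for changes and reporting of deviations, but does not make the 13.1 field a binding cap.
- **That subjects who fail the oral exam use up the enrolment number, so 44 should be defined as subjects assigned to a treatment sequence.** Section 13.6 is ambiguous. It says "Those individuals who give informed consent will be enrolled in the study", but of the oral exam that follows it says "If determined to be sufficient, the subject will then be fully enrolled in the study", and VII.j likewise places full enrolment after the exam. No section defines 44 by assignment. Doing so could mean consenting more than 44 people, which is not a free correction.

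**Conclusion.** The point holds as an error in a stated sample size: the 13.1 enrolment answer carries the completer requirement and conflicts with 44 in the same section, the abstract, VII.b and VII.h. If 38 were followed as the target, the plan's own drop-out range would leave about 34 to 30 completers, with power about 0.86-0.87 and 0.81-0.83 in place of 0.90.

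Those powers rest on two conditions: that enrolment stops at 38, and that the SD is the one that makes the plan's claim true at 38 pairs. They show the cost relative to the plan's own claim and do not estimate the trial's actual power, which cannot be checked without the SD.

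The practical weight is modest, since the right figure is in the same answer. The correction is still worth making because it is specific and nearly free.

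**What to change.** In section 13.1, change the answer to the enrolment question from 38 to 44. Keep 38 in the rationale only, as the number who must complete. That agrees with the abstract, VII.b and VII.h and adds no subjects beyond those the plan already names. The cost is one entry on the form, made through the amendment procedure in section 26.1 if the application is already approved.

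This removes the contradiction and nothing more. The adequacy of 44 for the 20% drop-out in VII.h, the difference between that 20% and the 10-20% in 13.1, and the missing SD and sidedness need their own resolution.
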